11.3 Safety Monitoring

Toxicities will be monitoring on an on-going basis. If a Grade 5 adverse event with attribution as possibly, probably, or likely related to treatment is observed, then accrual to the study will be placed on hold with review by the DSMB needed. Consideration for the event will include if the patient was naïve to anti-PD-1/PD-L1 therapy or previously-exposed to anti-PD-1/PD-1 therapy.

A key toxicity of concern is hepatotoxicity, with grade 4 interpreted as a clinically significant event. Historical rates of Grade 3-4 hepatotoxicity with PD-1/PD-L1 therapy are 5-30% and 3% with nelfinavir. For monitoring of this event, evidence suggesting that the observed rate of Grade 4 hepatotoxicity exceed a true rate of 15% would result in temporary closure of the study with expedited DMSC review. Evidence to suggest this will be based on the lower bound of an 80% confidence interval excluding 15%, pooling all patients on trial (regardless of disease type and prior exposure to anti-PD-1/PD-L1) and assessed within enrollment cohorts. As such, accrual to the study will be placed on hold if 2/2-4, 3/5-8, 4/9-12, 5/13-17, 6/18-21, 7/22-26, 8/27-31, 9/32-36, 10/37-41, 11/42-46, 12/47-51, 13/52-57, 14/58-62, 15/63-67, 16/68-73, 17/74-78, 18/79-84, 19/85-89, 20/90-95, 21/96-100, 22/101-106, 23/107-111, 24/112-117, or 25/118-120 patients are observed to have a Grade 4 hepatotoxicity event.

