11.0 STATISTICAL CONSIDERATIONS

11.1 Sample Size with Power Justification

The primary objective of this study is to evaluate the response rate in patients with non-small cell lung cancer (NSCLC), melanoma, or renal cell carcinoma (RCC) treated with nelfinavir, radiation therapy and anti-PD-1/PD-L1 therapy. Evaluation of this investigational therapy will be done in disease-specific cohorts separately evaluated by patients naïve to anti-PD-L1/PD-L1 therapy and those with disease refractory to anti-PD-1/PD-L1 therapy.

The total sample size for this study is 20 patients in each of the 6 cohorts (3 disease type by 2 anti-PD-1/PD-L1 exposure groups) for a total of 120 patients evaluable for response. The expected accrual rate is 30 patients per year. The design within each cohort is a single arm, single stage design. The sample size justification for each of the cohorts is follows. Sample size calculations were done using this calculator: <https://stattools.crab.org/Calculators/oneArmBinomial.html>.

Non-Small Cell Lung Cancer (NSCLC):

1. Checkpoint Naïve: In this cohort a true response rate of 50% or greater would be considered evidence of activity whereas a response rate of 25% or less (based on historical data) would not be considered of interest. With 20 patients, this study has 86% power to rule out a response rate of 25%, at the 1-sided 0.10 level if the true response rate were 50%. The observation of at least 8 responses (8/20; 40% ORR) would be

considered evidence to rule out a response rate of 25%. The exact power and type I error for this design are 87% and 10%, respectively.

2. Checkpoint refractory: In this cohort a true response rate of 25% or greater would be considered evidence of activity whereas a response rate of 5% or less (based on historical data) would not be considered of interest. With 20 patients, this study has 91% power to rule out a response rate of 5%, at the 1-sided 0.10 level if the true response rate were 25%. The observation of at least 3 responses (3/20; 15% ORR) would be considered evidence to rule out a response rate of 5%. The exact power and type I error for this design are 91% and 7.6%, respectively.

Melanoma:

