11.2 Analysis Plan

The primary analysis within each cohort will done on patients who receive at least one dose of nelfinavir, and anti-PD-1/PD-L1 therapy and at least one fraction of radiation. The safety analysis population will include all patients who receive at least one dose of any of the study drugs.

Binary endpoints (response, toxicity) will be summarized as proportions with associated 90% Clopper-Pearson confidence intervals. With 20 patients per cohort, binary proportions can be estimated to within 18% with 90% confidence. Any toxicity with true prevalence of at least 10% is likely to be observed (with 88% probability).

The distribution of time-to-event endpoints will be estimated using the method of Kaplan-Meier to derive estimates for median times and percentages at landmark times (e.g. 6 months). Confidence intervals for median times will be estimated using the Brookmeyer-Crowley method and for landmark times will be calculated using Greenwood's formula and based on a log-log transformation applied on the survival function.

A logistic regression model will be used to assess the association between response and factors such as smoking within each cohort. These associations will be summarized by odds ratios and associated confidence intervals and p-values. A Cox regression model will be used to assess the association between time-to-event outcomes (PFS,OS) and factors within each cohort. Similarly, these associations will be summarized by hazard ratios and associated confidence intervals and p-values.

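### The hepatotoxicity hold counts in 11.3 do not follow from the 80% confidence interval they are said to come from; they match a two-sided 90% Wilson interval

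*Combined protocol and SAP*

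**What the plan says.** Section 11.3 makes hepatotoxicity a key concern and takes 15% as the reference rate for Grade 4 events. The criterion for a hold is "based on the lower bound of an 80% confidence interval excluding 15" per cent. The interval type is not named, and the text does not say whether 80% is one-sided or two-sided.

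The next sentence gives the counts as the consequence of that criterion: "As such, accrual to the study will be placed on hold if 2/2-4, 3/5-8, 4/9-12, 5/13-17, 6/18-21, 7/22-26, 8/27-31, 9/32-36", continuing to "22/101-106, 23/107-111, 24/112-117, or 25/118-120 patients are observed to have a Grade 4 hepatotoxicity event". Every n from 2 to 120 is covered, which agrees with the planned total in 11.1.

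The criterion is applied "pooling all patients on trial (regardless of disease type and prior exposure to anti-PD-1/PD-L1) and assessed within enrollment cohorts".

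The only binomial interval named in the plan is in 11.2, for summaries: "Binary endpoints (response, toxicity) will be summarized as proportions with associated 90% Clopper-Pearson confidence intervals".

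**The concern.** The sentence and the list should be the same rule written twice. If they differ, someone who computes an 80% interval and someone who reads the list can reach different decisions on the same data.

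This is the count-based hold rule for the toxicity the protocol singles out. Crossing it closes the study temporarily and triggers expedited committee review. The plan gives no false-hold or detection probabilities that would show which evidence threshold was meant.

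**Working it through.** **Inputs.** Reference rate 0.15, the 80% level and the hold list (all 11.3); maximum n = 120 (11.1); 90% Clopper-Pearson (11.2). For each n from 2 to 120 (119 values), find the smallest x whose lower confidence limit exceeds 0.15 and compare it with the listed count.

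**Reproducing the list.** The Wilson lower limit exceeds 0.15 exactly when

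z = (x − 0.15n) / √(n × 0.15 × 0.85) > z_c,

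with z_c = 1.645 for a two-sided 90% interval and 1.282 for a two-sided 80% interval.

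| n | Listed count: z | One event fewer: z |
|---|---|---|
| 32 | 9: 4.2/2.020 = 2.079 | 8: 3.2/2.020 = 1.584 |
| 118 | 25: 7.3/3.879 = 1.882 | 24: 6.3/3.879 = 1.624 |
| 120 | 25: 7.0/3.912 = 1.790 | 24: 6.0/3.912 = 1.534 |

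In each row the listed count passes 1.645. One event fewer fails 1.645 but passes 1.282. Over all n, the smallest z at a listed count is 1.6501 and the largest z one event below is 1.6407. The list therefore fixes the Wilson level between 89.9% and 90.1%, and 90% Wilson matches at 119 of 119.

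**Trying 80%.** Sample sizes at which the list differs from each two-sided 80% interval:

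| 80% interval | List later | List earlier |
|---|---|---|
| Wilson | 99 | 0 |
| Agresti-Coull | 99 | 0 |
| Jeffreys | 98 | 0 |
| mid-P | 93 | 0 |
| Wilson, continuity-corrected | 57 | 1 |
| Wald | 50 | 0 |
| Clopper-Pearson | 49 | 2 |
| Wald, continuity-corrected | 8 | 22 |

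Reading 80% as a one-sided bound fits worse: the list is later at 99 to 117 sample sizes across six interval types and never earlier. Scanning levels from 70% to 95% in one-point steps for Wilson, Clopper-Pearson, Wald, continuity-corrected Wald and Jeffreys, only Wilson at 90% fits. The 90% Clopper-Pearson of 11.2 differs at 77, with the list earlier at all of them.

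No Clopper-Pearson level can give the list. That limit exceeds 0.15 when P(X ≥ x | n, 0.15) is below the one-sided error. The list holds at 2/4, where this tail is 0.1095, but does not hold at some counts with tails as low as 0.070.

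**Where decisions differ.**

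- 24/118: the 80% lower limit is 15.6% (Clopper-Pearson) and 16.0% (Wilson). For continuity-corrected Wald it is 0.2034 − 1.2816 × √(0.2034 × 0.7966/118) − 1/236 = 0.2034 − 0.0475 − 0.0042 = 15.2%. The other five also exceed 15%. The sentence says hold; the list needs 25.
- 8/32: 15.1% (Clopper-Pearson) and 16.6% (Wilson) meet the sentence; the list needs 9. Continuity-corrected Wald gives 0.25 − 0.0981 − 0.0156 = 13.6% and does not meet it.
- 2/4 and 3/8: the list holds, but the 80% Clopper-Pearson limits are 14.3% and 14.7%.

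**Size.** Probability of a hold by patient 120, by exact recursion over patients, pooled, with a look after each one from n = 2. Expected enrolment is capped at 120.

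| Rule | True 15% | True 20% | Expected enrolment at 20% |
|---|---|---|---|
| List | 32% | 72% | 56 |
| 80% Clopper-Pearson | 33% | 76% | 55 |
| 80% Wald | 36% | 77% | 53 |
| 80% Wilson | 53% | 86% | 36 |
| 80% Wilson, at least 2 events | 45% | 83% | 43 |
| 80% Wald, continuity-corrected | 26% | 70% | 64 |

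The fifth row is there because 80% Wilson already holds at 1/2 (z = 0.7/0.505 = 1.386). At a true 30% every rule holds with probability of at least 99.7%.

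**The case against.** The list gives an explicit count at every n, so staff can apply it without computing an interval. On that view only its description is wrong.

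The effect is also small under the one interval family the plan names. 80% Clopper-Pearson differs from the list by a single event, at 51 sample sizes, and moves the hold probability by about one point at a true 15% and about three at 20%. The 14-point difference arises only with 80% Wilson, which the plan never mentions.

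Within cohorts of 20, ordinary 80% Wald agrees with the list at every n from 2 to 21, and 80% Clopper-Pearson differs only at n = 4 and 8. A crossing means a temporary hold with review. A hold for treatment-related deaths, regular monitoring meetings and patient-level discontinuation criteria also exist.

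These points stand, and they limit the consequence. They do not remove the disagreement. 11.3 makes the interval the standard and the list its result, and nothing says the list prevails. The Wald agreement ends at n = 22, so it cannot rescue the pooled rule. The match with 90% Wilson is exact, but it is a numerical match and does not show what was intended.

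**Conclusion.** The concern holds. The sentence and the list in 11.3 are different rules: no 80% interval tried, one-sided or two-sided, gives the list, and a two-sided 90% Wilson interval gives it at every n from 2 to 120.

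The direction and size of the gap depend on the unnamed interval type. The list is more lenient than 80% Wilson at 99 sample sizes (by one event at 85, by two at 14). Against 80% Clopper-Pearson it is more lenient at 49, all from n = 22 upward, and stricter at 2. Against continuity-corrected 80% Wald it is stricter at 22, between n = 4 and n = 62, and more lenient at 8. At a true 20%, moving from the list to an 80% rule changes the hold probability by between −2 points (continuity-corrected Wald) and +14 points (Wilson).

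These probabilities assume independent patients with a common event rate, pooled counting, and a look after every patient. The finding does not show that patients are less protected than intended, because the intended threshold cannot be recovered from the documents.

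**What to change.** Reconcile the sentence and the list in 11.3. State the level, the sidedness and the interval type together, and have the sponsor and the monitoring committee confirm which threshold was meant. There are two routes:

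- Keep the list and describe it as the lower limit of a two-sided 90% Wilson interval. Operation does not change.
- Keep 80%, name the interval and replace the list. Two-sided 80% Clopper-Pearson gives 2/2-3, 3/4-7, 4/8-12, 5/13-17, 6/18-22, 7/23-27, 8/28-32 and so on to 24/117-120. Two-sided 80% Wilson gives 1/2, 2/3-5, 3/6-10, 4/11-14, 5/15-19, 6/20-24, 7/25-29, 8/30-35 and so on to 24/120.

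Either way, add the hold probabilities at true rates of 15%, 20% and 30%.

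The cost is a text or list amendment confirmed by the committee, with no added patients or procedures. Changing the list also changes false holds. At a true 10%, the hold probability by patient 120 goes from 9.4% to 7.9% under 80% Clopper-Pearson, and to 26% under 80% Wilson (15% if at least two events are required).

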6.1 Nelfinavir treatment dosage and administration

Nelfinavir will be available in Investigational Drug Services (IDS) at the University of Washington and Seattle Cancer Care Alliance. When a subject is enrolled, the drug will be obtained and dispensed from IDS. It is stored at room temperature. Nelfinavir will be self-administered at a dose of 1250 mg PO BID and the patient will administer at home. This dosing is based upon the results of our phase I trial. (47) All subjects will begin taking daily oral nelfinavir 7 to 14 days prior to the start of PD1/PDL1 immune checkpoint inhibitor. Nelfinavir will be continued for a total of 11-12 weeks, depending on when Nelfinavir was initiated and when the first dose of PD1/PDL1 immune checkpoint inhibitor is. This corresponds to the duration of nelfinavir administration in the phase I trial. (47) Subjects will not receive any additional nelfinavir after the 12th week of nelfinavir, or a total of 3 bottles. The 7-14 days of nelfinavir prior to PD1/PDL1 immune checkpoint inhibitor commencement are based on the known pharmacokinetics of the drug that has shown suppression of PI-3 kinase within three days after the administration of nelfinavir (see background information). Subjects will be asked to maintain a drug diary to assess compliance with administration of nelfinavir (appendix 14.3)

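### The Grade 4 hepatotoxicity hold list has no observation window, so treated patients with incomplete follow-up count as fully observed and event-free, which delays the hold but rarely loses it

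*Combined protocol and SAP*

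**What the plan says.** Section 11.3 seeks "evidence suggesting that the observed rate of Grade 4 hepatotoxicity exceed a true rate of 15" per cent, judged by the "lower bound of an 80% confidence interval excluding 15" per cent, and turns this into hold counts that begin "2/2-4, 3/5-8, 4/9-12, 5/13-17, 6/18-21, 7/22-26" and end at 25 events among 118 to 120 patients. The assessment is made by "pooling all patients on trial (regardless of disease type and prior exposure to anti-PD-1/PD-L1) and assessed within enrollment cohorts". Timing is open: "Toxicities will be monitoring on an on-going basis".

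No section adds a follow-up requirement. Section 6.3 makes any treated patient evaluable for toxicity. Section 11.2 admits a patient to the safety population after one dose of any study drug. Section 6.11 calls a patient with no checkpoint inhibitor dose non-evaluable, but for replacement, and 11.3 does not refer to it.

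The exposure facts come from elsewhere. Section 11.1: "The expected accrual rate is 30 patients per year". Section 6.1: "All subjects will begin taking daily oral nelfinavir 7 to 14 days prior to the start of PD1/PDL1 immune checkpoint inhibitor", and "Nelfinavir will be continued for a total of 11-12 weeks".

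**The concern.** Events divided by patients estimates the event rate only if every patient in the denominator has been observed for the period in which events occur. Under continuous monitoring with steady accrual, some patients have always only just started. The rule counts them as full event-free observations, which lowers the apparent rate and raises the number of events required.

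This matters because the list is the trial's only rate-based toxicity boundary, hepatotoxicity is the toxicity that 11.3 singles out, and section 7.1 acknowledges that the combined effects of nelfinavir and the inhibitors are not fully studied. A late hold means more patients treated before the review that the rule is meant to trigger.

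**Working it through.** **The printed list.** It covers n = 2 to 120 without gaps. It does not follow from an 80% interval by any standard method tried (Clopper-Pearson at 10% per tail differs at 51 of 119 values). It matches a Wilson lower bound with 5% per tail at all 119. That is a separate matter; the list is taken here as printed.

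**The list with every patient fully observed** (exact sequential binomial calculation):
- Hold by patient 20: 8.5% at a true rate of 10%, 57.4% at 25%, 73.6% at 30%.
- Any hold by patient 120: 9.4% at a true 10%, 32% at a true 15%.

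**Patients incompletely observed at any time** = annual accrual × weeks / 52.
- 12-week period: 30 × 12/52 = 6.9.
- Run-in of 1 to 2 weeks: 30 × 1/52 = 0.6 to 30 × 2/52 = 1.2.

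**Effect on the threshold.** Suppose 12 patients are fully observed, all events are among them, and 7 more are pending.
- The 12 alone: 4 events trigger a hold (4/9-12).
- As written: n = 12 + 7 = 19, so 6 events are needed (6/18-21).
- Weighted, with the pending patients half-way on average: n = 12 + 7 × 0.5 = 15.5, rounded up to 16, so 5 are needed (5/13-17).

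Weighting does not always change the threshold. With 9 observed and 7 pending, n is 16 as written and 9 + 3.5 = 12.5, rounded up to 13, when weighted. Both need 5.

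**Delay by simulation.** Inputs from the documents are the printed list, 30 patients a year and a maximum of 120. Assumptions are random (exponential) gaps between enrolments, first study drug at enrolment, and event onset uniform over a period equal to the observation window. As written, n is everyone enrolled. Weighted, n is the number of patients with an event plus the sum of window fractions completed by event-free patients, rounded up.

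| True rate | Onset and window | Measure | As written | Weighted |
|---|---|---|---|---|
| 25% | 6 weeks | median enrolled at hold | 24 | 19 |
| 25% | 12 weeks | median enrolled at hold | 31 | 21 |
| 25% | 16 weeks | median enrolled at hold | 38 | 24 |
| 30% | 12 weeks | hold by patient 20 | 50% | 65% |
| 25% | 12 weeks | any hold | about 94% | about 95% |
| 15% | 12 weeks | any hold | 20-23% | 27-30% |
| 10% | 12 weeks | any hold | 3% | 7-9% |

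Medians move by a patient or two between runs.

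**Which patients cause the delay.** In a variant with onset uniform over weeks 2 to 12 and a true rate of 25%, the mean number enrolled at the hold is 44.6 as written, 41.3 if only patients in their first two weeks are left out, and 35.5 if only completed 12-week windows count. Leaving out the run-in recovers 44.6 − 41.3 = 3.3 of 44.6 − 35.5 = 9.1 patients. Most of the delay comes from patients already on the combination with short follow-up.

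**The case against.** The strongest reply is that the missing window costs little. The hold is postponed rather than lost: at a true 25% it eventually fires in over 92% of trials under either denominator (12 weeks), and at 30% in over 99%. A single related Grade 5 event also triggers a hold under 11.3, and section 8 provides DSMB review of the first 2 or 3 patients after re-opening and quarterly meetings after that. All of this stands and limits the severity. None of it gives the rate boundary a properly observed denominator.

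The size also rests on an onset time that the documents do not give, and the weighting assumes the same uniform onset as the simulation that tests it. That stands too. The gap shrinks to about five patients with a 6-week window, but the delay appeared in every setting tried at true rates of 25% and 30%.

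The words on pooling in 11.3 may be meant only to combine strata, not to define n as everyone enrolled. Sections 6.3 and 11.2 would then exclude untreated patients. That is a fair reading, though 11.3 does not state it. It leaves the main problem untouched, because one dose satisfies both sections.

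Two stronger readings are not supported. A reader might infer that newly enrolled and run-in patients are the main cause. They are about 1 of the 7, they are under observation because section 7.2 records adverse events from the start of nelfinavir, and 11.3 itself quotes a 3% Grade 3-4 rate for that drug. A reader might also set the roughly 50% chance of a hold by patient 20 at a true 30% against the list's 74%. The 74% assumes that events are seen at once, which no denominator rule can achieve. The fair comparison is 50% against 65%.

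**Conclusion.** The point holds as a moderate design weakness. Section 11.3 as written treats patients with incomplete follow-up as fully observed, and no other section corrects this. At a true rate of 25%, about 5 to 14 more patients are enrolled before the median hold (24 − 19 = 5 at 6 weeks, 31 − 21 = 10 at 12 weeks, 38 − 24 = 14 at 16 weeks). These figures depend on uniform onset, a window that matches it, and accrual at the planned rate. The direction does not depend on the particular window length. The documents do not support saying that the boundary fails, since it nearly always fires in the end when the true rate is well above 15%.

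**What to change.** In 11.3:
1. State that n counts only treated patients.
2. Define a hepatotoxicity observation window from first study drug. The sponsor should justify its length, since the inhibitor continues after nelfinavir ends.
3. Count each patient with an event as 1, and each event-free patient by the fraction of the window completed (1 when complete).
4. Round the total up to a whole number and apply the printed list to it.
5. State the operating characteristics, including those at the 15% reference rate.

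The work is a short wording change and one extra column in the DSMB report. The statistical cost is more temporary holds at acceptable rates. With a 12-week window, any hold rises from about 3% to 7-9% at a true 10%, and from about 20-23% to 27-30% at a true 15%. Both stay at or below the list's own 9.4% and 32% under full observation. If events cluster earlier than the window assumes, they do not: with onset within 6 weeks of a 12-week window, the figures are about 12% and 36%. Counting only completed windows is an alternative. In the variant with onset over weeks 2 to 12, it gave a median of 22 enrolled against 33 as written at a true 25%, and raised any hold at a true 15% from 18.8% to 31.4%.

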11.4 Accrual

Projected Target Accrual
ETHNIC AND GENDER DISTRIBUTION CHART

TARGETED / PLANNED ENROLLMENT: Number of Subjects			
Ethnic Category	Sex / Gender		
	Females	Males	Total
Hispanic or Latino	8	10	18
Not Hispanic or Latino	42	60	102
Ethnic Category Total of All Subjects*	50	70	120
Racial Categories			
American Indian / Alaska Native	4	4	8

Asian	4	4	8
Native Hawaiian or Other Pacific Islander	0	0	0
Black or African American	4	4	8
White	38	58	96
More Than One Race	0	0	0
Racial Categories: Total of All Subjects*	50	70	120

12.0 INVESTIGATOR OBLIGATIONS

The PI is responsible for the conduct of the clinical trial at the site and is responsible for personally overseeing the treatment of all study subjects. The PI must assure that all study site personnel, including sub-Investigators and other study staff members, adhere to the study protocol and to all applicable regulations and guidelines regarding clinical trials both during and after study completion.

